9.3.3. Risks Associated with the Participation in the Clinical Investigation

Compared to standard clinical practice, additional risks associated with the participation in RGnCON are risks related to:

- **The use of RGn550**

Anticipated ADEs of RGn550 are described above (section 9.3.2).

Moreover, as mentioned in RGn550's investigator brochure, a risk management process specific to RGn550 was put in place by REGEnLIFE in accordance with NF EN ISO 14971-2019.

- **The automated oculomotor/oculopostural tests and the TMT A & B**

Identified risks related to the conduct of such tests are symptoms such as fatigue, headache and dizziness, which are related to the fact that treated patients have a concussion. These symptoms remain acceptable as they are usual symptoms of concussions, expected to remain minor within this context.

- **The stabilometric test**

The only risk that has been identified as related to the use of the stabilometry platform is a risk of stumble/fall of the patient. However, this risk remains very unlikely considering the reduced height of the platform and the fact that investigators, which are healthcare professionals, will help and support patients during the whole stabilometric process.

- **The blood sampling procedure**

Risks related to the blood sampling procedure are pain, hematoma at the puncture site, lack of blood reflux, reflex syncope as well as contamination by hepatitis C, C or HIV for the person performing the sampling. These risks are mitigated by the fact that a nurse will be perform the sampling.

No risks were identified as being related to the use of the Sport Concussion Assessment Tool – 5th edition (SCAT5) symptom evaluation tool.

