Following this, the patient will evaluate his/her symptoms using the **SCAT5 symptom evaluation tool**. The patient will rate the intensity of every symptom from 0 (none) to 6 (severe) using a form. This will allow to calculate the total number of symptoms (out of 22) and the symptom severity score (out of 132) (see Appendix 12.3).

A **blood sample** will also be obtained from the patients by a nurse. The blood sample analysis will be performed by Montpellier Neuroscience Institute (*Institut de Neuroscience de Montpellier*) following the institute standard practice.

During the visit, the patients will be **randomized** in a 1:1 ratio to the 5 Hz group or 10 Hz group using the centralized Interactive Web Response System (IWRS) incorporated into the eCRF. A block randomization method will be used. Only patients will be blinded to their assigned treatment.

Depending on their assigned group, the patients will then be **treated** with one of the 5 Hz RGn550 devices or one of the 10 Hz RGn550 devices for 20 min. To perform the treatment, the principal investigator will follow the below instructions:

- Make the patient comfortable.
- Install the helmet on the patient's head, taking care not to bump it with the modules.
- Lightly tighten the soft helmet holding wire and check the positions of the modules. Each module can be moved slightly to adjust its position.
- On the control unit, in the menu on the left, choose the option 'Program' and choose the proposed treatment
- Finally press the red arrow to start the treatment.

A countdown is displayed on the screen indicating the time remaining until the end of the treatment session. At each treatment session, the principal investigator will fulfil a treatment sheet associated with the used device and mention the number of the treated patient, date of treatment, number of

treatment session and duration of treatment. To stop the treatment, the principal investigator will press the red button with a cross inside that is displayed on the screen (a confirmation message will be displayed to avoid any manipulation error).

Following treatment, the investigators will:

- **Perform the following tests** following the methodology described above:
 - NPC
 - Cover test
 - Maddox rod test
 - Static stabilometric test
- **Collect any AEs and DDs** that occurred during the visit.

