9.5.5.2. Second Treatment Session Visit (D7)

This visit will occur at D7 and will correspond to the second treatment session.

Before treatment, the investigators will **collect any AEs** that occurred since the last visit.

Following that, they will **check** that:

- Patients did not have a **second concussion** between the first and second treatment sessions, as this could impact the performance evaluations
- Patients did not become **contraindicated** to RGn550 treatment between the first and second treatment sessions

If that's the case, the second treatment session will not be performed nor any of the remaining performance evaluations described below.

If applicable, before treatment:

- The investigators will **perform the following tests** following the methodology described above:
 - NPC
 - Cover test
 - Maddox rod test
 - Static stabilometric test
- The patient will be asked to evaluate the intensity of his/her symptoms using the SCAT5 symptom evaluation tool.

The patients will then be **treated** for 20 min, as per their assigned group and using the same RGn550 device that was used at D0.

Following treatment, the investigators will:

- **Perform the following tests:**
 - NPC
 - Cover test
 - Maddox rod test
 - Static stabilometric test
 - TMT A&B
- **Collect any AEs and DDs** that occurred during the visit.
- Give the patient a **SCAT5 symptom evaluation tool form** for remote completion by the patient at D14.

| | | |
|--------|---|---|
| RGnCON | Clinical Investigation Plan Version 2.0 - 11 August 2022 |  |
|--------|---|---|

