9.5.5.3. Remote Visit (D14)

Seven days after the second treatment session, the investigators will **call the patients** to remind them to complete the SCAT5 symptom evaluation tool and bring the form with them during their next visit at D52.

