12.2. Trail Making Test

12.2.1. Part A

12.2.2. Part B

12.3. SCAT5 Symptom Evaluation Tool

**ÉTAPE 2: ÉVALUATION
DES SYMPTÔMES**

Vous devez donner le formulaire des symptômes à l'athlète et lui demander de lire ce paragraphe d'instructions à voix haute avant de remplir l'échelle. Pour l'évaluation de base, l'athlète doit donner une note à ses symptômes selon son ressenti habituel. Pour l'évaluation post-traumatisme, l'athlète doit donner une note à ses symptômes actuels.

Cochez la case correspondante: Base Post-traumatisme

Donnez le formulaire à l'athlète

| | RAS | Léger | Modéré | Important | | |
|--|-----|-------|--------|-----------|-----|---------|
| Maux de têtes | 0 | 1 | 2 | 3 | 4 | 5 6 |
| «Pression dans le crâne» | 0 | 1 | 2 | 3 | 4 | 5 6 |
| Douleur dans le cou | 0 | 1 | 2 | 3 | 4 | 5 6 |
| Nausée ou vomissement | 0 | 1 | 2 | 3 | 4 | 5 6 |
| Vertiges | 0 | 1 | 2 | 3 | 4 | 5 6 |
| Vision trouble | 0 | 1 | 2 | 3 | 4 | 5 6 |
| Problèmes d'équilibre | 0 | 1 | 2 | 3 | 4 | 5 6 |
| Sensibilité à la lumière | 0 | 1 | 2 | 3 | 4 | 5 6 |
| Sensibilité au bruit | 0 | 1 | 2 | 3 | 4 | 5 6 |
| Sensation d'être ralenti.e | 0 | 1 | 2 | 3 | 4 | 5 6 |
| Sensation d'être «dans le brouillard» | 0 | 1 | 2 | 3 | 4 | 5 6 |
| «Ne pas se sentir normal.e» | 0 | 1 | 2 | 3 | 4 | 5 6 |
| Problèmes de concentration | 0 | 1 | 2 | 3 | 4 | 5 6 |
| Problèmes de mémoire | 0 | 1 | 2 | 3 | 4 | 5 6 |
| Fatigue ou manque d'énergie | 0 | 1 | 2 | 3 | 4 | 5 6 |
| Confusion | 0 | 1 | 2 | 3 | 4 | 5 6 |
| Somnolence | 0 | 1 | 2 | 3 | 4 | 5 6 |
| Sensibilité | 0 | 1 | 2 | 3 | 4 | 5 6 |
| Irritabilité | 0 | 1 | 2 | 3 | 4 | 5 6 |
| Tristesse | 0 | 1 | 2 | 3 | 4 | 5 6 |
| Nervosité ou anxiété | 0 | 1 | 2 | 3 | 4 | 5 6 |
| Difficultés à s'endormir (si applicable) | 0 | 1 | 2 | 3 | 4 | 5 6 |
| Nombre total de symptômes: | | | | | | sur 22 |
| Degré de sévérité des symptômes: | | | | | | sur 132 |
| Vos symptômes s'aggravent-ils pendant une activité physique? | | | | | 0 N | |
| Vos symptômes s'aggravent-ils pendant une activité mentale? | | | | | 0 N | |
| Si 100 % correspond à une sensation normale, à combien de pour cent vous sentez-vous normal.e? | | | | | | |

Si la réponse n'est pas 100%, pourquoi?

Rendez le formulaire à l'examinateur.trice

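### SCAT5 is rated after symptom-risk tests at D0 but remotely with no tests at D14, so change from D0 may overstate symptom improvement by an unknown amount

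*Protocol*

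**What the plan says.** **D0 (Protocol 9.5.5.1).** The section describes NPC, cover test, Maddox rod, stabilometry and TMT A&B, and then continues: "Following this, the patient will evaluate his/her symptoms using the" SCAT5 tool. Here the order is explicit.

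**D7 (Protocol 9.5.5.2).** Before treatment, NPC, cover, Maddox and stabilometry come first in the list. The next item reads: "The patient will be asked to evaluate the intensity of his/her symptoms using the SCAT5 symptom evaluation tool". No word fixes the sequence. TMT A&B is done only after treatment.

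**D52 (Protocol 9.5.5.4).** SCAT5 appears after the same four tests and before the blood sample, which is placed last. TMT is not done.

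**D14 (Protocol 9.5.5.3).** The investigators phone patients "to remind them to complete the SCAT5 symptom evaluation tool and bring the form with them during their next visit at D52". No test is performed.

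**Risk of the tests (Protocol 9.3.3).** For the oculomotor/oculopostural tests and the TMT: "Identified risks related to the conduct of such tests are symptoms such as fatigue, headache and dizziness". The section ties these symptoms to the concussion itself and adds: "These symptoms remain acceptable as they are usual symptoms of concussions, expected to remain minor within this context". For stabilometry it names only a stumble or fall.

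**The form (Protocol 12.3).** After an injury, "l'athlète doit donner une note à ses symptômes actuels", that is, the athlete rates current symptoms. Headache, dizziness and fatigue are three of its 22 items.

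**Analysis.** Protocol 9.6.3.2 and SAP 8.5.1.3 fit a linear mixed model to the four timepoints with group, period and their interaction. The SAP adds the SCAT5 baseline as a covariate. A note at the end of SAP 8.5.1.3 adds a D0 versus D52 analysis of all patients, with period as its only fixed effect. Neither document sets a rest period before SCAT5, asks for it to come first, or refers to the setting of the rating.

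**The concern.** A scale of current symptoms records whatever the patient feels at that moment, including any fatigue, headache or dizziness brought on by tests just completed. If the text order is followed, the four ratings are taken under three conditions: after oculomotor tests plus TMT (D0), after oculomotor tests only (D7, D52), and after no tests (D14). The heaviest battery precedes the baseline.

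Any test effect would therefore push change from baseline towards apparent improvement, most of all at D14, which is the rating behind the objective on symptoms 7 days after the second session. The condition is fixed by visit, so no model term can separate it from the period effect; it can only be dealt with when the data are collected. Within-patient change carries weight here because there is no sham group, and Protocol 9.2.3 concedes that the placebo effect is not controlled.

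**Working it through.** The plan gives no figure for SCAT5, so there is none to reproduce. Its only design figure concerns ADEs (1 - 0.96^50 = 0.870, agreeing with the stated 0.87) and does not bear on this point.

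**Ceiling, from the form**

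- Severity: 3 named items x 6 points = 18 of 132 (13.6%).
- Count: 3 of 22 symptoms (13.6%). An item already present before the tests adds nothing to the count.

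**Offsets**

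Let e be the rise in severity from the oculomotor tests and t the extra rise from the TMT. Both are assumptions: the documents give no size, and either may be zero. Stabilometry is given no offset because 9.3.3 names only a fall risk for it. Taking the text order as the order followed, observed score = true score + offset:

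| Visit | Tests before SCAT5 | Offset |
|---|---|---|
| D0 | oculomotor, stabilometry, TMT | e + t |
| D7 | oculomotor, stabilometry | e |
| D14 | none | 0 |
| D52 | oculomotor, stabilometry | e |

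**Bias in change, with constant offsets**

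- D0 to D7: e - (e + t) = -t
- D0 to D14: 0 - (e + t) = -(e + t)
- D0 to D52: e - (e + t) = -t
- D14 to D52: e - 0 = +e

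A negative value means improvement is overstated. In severity points, for assumed values:

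| e | t | D0 to D7 | D0 to D14 | D0 to D52 | D14 to D52 |
|---|---|---|---|---|---|
| 0 | 0 | 0 | 0 | 0 | 0 |
| 1 | 0 | 0 | -1 | 0 | +1 |
| 3 | 0 | 0 | -3 | 0 | +3 |
| 3 | 1 | -1 | -4 | -1 | +3 |
| 3 | 3 | -3 | -6 | -3 | +3 |
| 6 | 3 | -3 | -9 | -3 | +6 |

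For illustration, with an assumed true fall of 5 points from D14 to D52, e = 3 would show a fall of 5 - 3 = 2, and e = 6 a rise of 6 - 5 = 1.

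**If provocation fades with recovery.** Suppose t = 0 and the oculomotor offset is 3 at D0, 2 at D7 and 0 at D52. The bias is then 2 - 3 = -1 at D7 and 0 - 3 = -3 at D52, where constant offsets would have given zero.

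**Which analyses are touched**

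- *Within-patient course over the four visits:* affected as above.
- *SAP pooled D0 versus D52 analysis:* affected by t and by any fading. It does not use D14.
- *5 Hz versus 10 Hz difference:* both groups follow the same schedule. If mean provocation is equal in both, the offset cancels in the difference at each visit.

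**The case against.** The strongest case against the point is that the documents support less than a reader might infer. Several stronger readings should be set aside.

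- *SCAT5 is fixed directly after the tests at all three on-site visits.* Only D0 is explicit. At D7 and D52 the order rests on listing, and the schedule table gives no order within a visit. A site could rate SCAT5 first at those visits without deviating. This stands, although an unspecified order is itself an uncontrolled condition.
- *The protocol says the tests provoke symptoms.* It lists them as a risk, attributes them to the concussion and expects them to be minor. This stands: the mechanism is plausible from the sponsor's own text, but its size is unknown.
- *A given number of points of improvement, such as 3 to 6, is artefact.* That would assume a rise of 1 to 2 points on all three items in every patient. Nothing in the documents supports this, or excludes smaller effects or none.
- *Improvement at D7 and D52 must be overstated.* A constant oculomotor offset cancels there. Bias at those visits needs a TMT effect or fading provocation.
- *The comparison of frequencies is compromised.* It is not biased under equal provocation, and the SAP template shows p-values only for that comparison.

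It can also be said that within-group falls could not be credited to the device anyway: there is no sham, and Protocol 9.2.1.1.3 says adult symptoms typically resolve in 10 to 14 days. That limits the consequence. It does not justify an avoidable bias in the same direction in a course that will be reported.

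**Conclusion.** The point holds as a possible, directional bias of unknown size in the within-patient symptom course. The contrasts with D14 are the most exposed: -(e+t) against D0 and +e towards D52. Change from D0 to D7 and to D52, including the SAP's pooled D0 to D52 analysis, is biased by -t with constant offsets, and by more if provocation fades as patients recover. For the three named items the effect cannot exceed 18 of 132 points or 3 of 22 symptoms; the actual size may be small or zero.

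The conclusion assumes that sites followed the text order at D7 and D52, and that offsets add to the true score. It does not reach the randomised 5 Hz versus 10 Hz difference as long as provocation is equal in the two groups. The reason to act is that the bias, if present, favours apparent improvement and is cheap to reduce.

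**What to change.** In Protocol 9.5.5.1, 9.5.5.2 and 9.5.5.4, state that SCAT5 is the first assessment at each on-site visit, before NPC, cover test, Maddox rod, stabilometry and TMT. Where HIA3 is done at the same D0 visit, SCAT5 should also precede its test components where feasible. HIA3 contains cognitive, balance, gait and eye-movement tests, and any effect of these would, like t, load on D0 alone.

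This would reduce the difference from D14 but not remove it: D14 remains a home rating with whatever activity came before it, so the four ratings should not be described as fully matched.

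The cost is a change of sequence and of the visit worksheet, carried by a protocol amendment. It adds no time, staff or procedure.

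SAP version 2.0 follows a data review, so reordering cannot help data already collected. For those data, report the order actually used at each visit, and state that contrasts with D14 and change from D0 need caution. The revised order should carry into the sham-controlled follow-on work foreseen in Protocol 9.2.3.

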9.5.5.2. Second Treatment Session Visit (D7)

This visit will occur at D7 and will correspond to the second treatment session.

Before treatment, the investigators will **collect any AEs** that occurred since the last visit.

Following that, they will **check** that:

- Patients did not have a **second concussion** between the first and second treatment sessions, as this could impact the performance evaluations
- Patients did not become **contraindicated** to RGn550 treatment between the first and second treatment sessions

If that's the case, the second treatment session will not be performed nor any of the remaining performance evaluations described below.

If applicable, before treatment:

- The investigators will **perform the following tests** following the methodology described above:
 - NPC
 - Cover test
 - Maddox rod test
 - Static stabilometric test
- The patient will be asked to evaluate the intensity of his/her symptoms using the SCAT5 symptom evaluation tool.

The patients will then be **treated** for 20 min, as per their assigned group and using the same RGn550 device that was used at D0.

Following treatment, the investigators will:

- **Perform the following tests:**
 - NPC
 - Cover test
 - Maddox rod test
 - Static stabilometric test
 - TMT A&B
- **Collect any AEs and DDs** that occurred during the visit.
- Give the patient a **SCAT5 symptom evaluation tool form** for remote completion by the patient at D14.

| | | |
|--------|---|---|
| RGnCON | Clinical Investigation Plan Version 2.0 - 11 August 2022 |  |
|--------|---|---|

9.5.5.3. Remote Visit (D14)

Seven days after the second treatment session, the investigators will **call the patients** to remind them to complete the SCAT5 symptom evaluation tool and bring the form with them during their next visit at D52.

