9.5.5.4. Follow-up Visit (D52)

During this visit, which will occur 45 days after the second treatment session, no treatment will be performed.

The investigators will:

- Collect the **SCAT5 symptom evaluation tool form** that was completed by the patient at D14
- **Collect any AEs** that occurred since the last visit
- **Check** that, between the first and second treatment sessions, patients did not have a **second concussion**. If that's the case, remaining performance evaluations won't be performed.
- If applicable, **perform the following tests**:
 - NPC
 - Cover test
 - Maddox rod test
 - Static stabilometric test

The patient will be asked to evaluate the intensity of his/her symptoms using the SCAT5 symptom evaluation tool.

Finally, a **blood sample** will be obtained by the nurse.

Once all these evaluations have been conducted and all the required data have been collected, a treatment session may be offered to patients who did not become **contraindicated** to RGn550 treatment after the second treatment session.

Patients who became contraindicated to RGn550 treatment or had a second concussion between the first and second treatment session will not come on site for this visit since no further performance evaluations will be performed for these patients. However, the principal investigator will call them on D52 to collect any AEs that occurred since the last visit.

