9.5.5.5. Schedule

Table 2 below summarizes procedures and evaluations to perform at each visit.

| | |
|--|--------------|
| 2022.08.11_RGnCON_Prot_Final_V2.0_clean_public | Page 45 / 82 |
|--|--------------|

| | | |
|--------|---|---|
| RGnCON | Clinical Investigation Plan Version 2.0 - 11 August 2022 |  |
|--------|---|---|

Table 2: Schedule of procedures and evaluations

| | D0 | | D7 | | D14 (remote) | D52 |
|--|------------------|-----------------|------------------|-----------------|-----------------|-----|
| | Before treatment | After treatment | Before treatment | After treatment | | |
| Patient information / Informed consent | X | | | | | |
| Eligibility criteria | X | | | | | |
| Pregnancy test for women of childbearing potential | X | | | | | |
| Randomization | X | | | | | |
| Demographic and clinical data | X | | | | | |
| NPC | X | X | X | X | | X |
| Cover test | X | X | X | X | | X |
| Maddox rod test | X | X | X | X | | X |
| Stabilometric test | X | X | X | X | | X |
| TMT A&B | X | | | X | | |
| SCAT5 symptom evaluation tool | X | | X | | X | X |
| Blood sampling | X | | | | | X |
| 20-min treatment session | X | | X | | | |
| Collection of AEs and DDs that previously occurred | | X | X | X | | X |

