9.6. Statistical Considerations

9.6.1. Sample Size Justification

For a sample size of 50 patients, the probability of observing at least one ADE will be 0.87 considering a probability of ADE of 0.04. The sample size calculation was performed with SAS® v9.4.

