9.6.3. Statistical Analysis

Full details related to statistical analysis will be provided in the Statistical Analysis Plan.

The statistical analysis will be performed using SAS® Viya v9.4 (or a more recent version).

The global significance level (type I error rate) will be set at $\alpha = 0.05$ (two-sided). Adjustment for multiplicity is not applicable for the primary endpoint and no adjustment for multiplicity is planned for secondary endpoints.

Continuous data will be described by the number of missing data, number of data analyzed, mean, standard deviation, median, Q1, Q3, minimum, maximum.

Categorical data will be described by the number of missing data, frequencies and percentages of patients in each modality. The percentage of patients will be calculated once missing data are excluded from the denominator.

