9.6.3.1. Primary Endpoint Analysis

The proportion of subjects with at least one ADE will be calculated along with the 95% exact Clopper-Pearson confidence interval in the FAS, by treatment groups and overall.

Of note, a lost to follow-up rate of 10% is anticipated. If this rate is higher, an analysis of the primary endpoint using percentage of patient-years will be considered in the Statistical Analysis Plan.

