#### 8.4.4. Adverse device events by MedDRA SOC and MedDRA PT

For all ADEs, a descriptive analysis will be provided by MedDRA SOC and MedDRA PT, by randomization arm and overall.

For all ADEs occurring during the first session (at D0), a descriptive analysis will be provided by MedDRA SOC and MedDRA PT, by randomization arm and overall.

For all ADEs occurring during the second session (at D7), a descriptive analysis will be provided by MedDRA SOC and MedDRA PT, by randomization arm and overall.

The same template as above (i.e. for Adverse events) will be used.

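### ADEs that start after the patient leaves the D7 visit have no scheduled AE question until D52, although investigators already telephone patients at D14

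*Protocol*

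**What the plan says.** The primary endpoint is ADE incidence over the whole investigation (Protocol 9.5.4.1). Its analysis is a per-patient yes/no: "The proportion of subjects with at least one ADE will be calculated along with the 95% exact Clopper-Pearson confidence interval" (Protocol 9.6.3.1).

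AEs are asked about at four points:

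- **D0, after treatment:** on site, same day (9.5.5.1).
- **D7, before treatment:** events since D0 (9.5.5.2).
- **D7, after treatment:** on site, same day (9.5.5.2).
- **D52:** any AEs "that occurred since the last visit" (9.5.5.4).

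The D14 contact is a telephone call by the investigators. Its only stated purpose is "to remind them to complete the SCAT5 symptom evaluation tool and bring the form with them during their next visit at D52" (9.5.5.3). Table 2 agrees; the fifth cell, D14, is empty: "Collection of AEs and DDs that previously occurred | | X | X | X | | X". The synopsis schedule has the same blank.

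Protocol 9.13.3 requires every AE and DD from inclusion to the end of the 52-day follow-up to be recorded, and reported to the sponsor within 3 calendar days of the investigator becoming aware.

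The SAP adds tables by session, for example: "For all ADEs occurring during the second session (at D7), a descriptive analysis will be provided by MedDRA SOC and MedDRA PT" (SAP 8.4.4). The notes to SAP 6.2.1 assign an ADE to a session only if its start date is the date of D0 or of D7.

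**The concern.** The two sessions are followed by unequal ascertainment. A delayed effect of session 1 is asked about within a week. A delayed effect of session 2 may wait more than six weeks, although the site speaks to the patient halfway through the second week. Protocol 9.3.2 expects no severe ADEs, so the events at stake are the milder ones that a patient could forget, or be unable to date, by D52. The completed D14 symptom form does not help earlier, because it is handed in only at D52.

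Three things are at stake:

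- **The primary estimate.** A patient whose only ADE is forgotten is counted as having none, so the overall proportion could be too low.
- **Timeliness.** The 3-day reporting clock starts at awareness, which for an unprompted event may be D52. Section 9.15.1 lets ADE incidence or severity prompt suspension, and 9.13.6 provides no data safety monitoring board.
- **Dating.** SAP 7.5 replaces a completely missing onset date with the date of the first session. A missing day becomes the first of the month, moved up to the first-session date if that is later. Nothing in the SAP exempts the by-session tables, so an ADE that followed session 2 but can no longer be dated may be counted in the D0 table.

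There is also a small ambiguity. Section 9.5.5.3 calls the D14 contact a remote visit, so asking at D52 about events since the last visit could be read as leaving out D7 to D14.

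**Working it through.** **Inputs from the documents.** N = 50 and ADE probability 0.04 (Protocol 9.6.1); sessions at D0 and D7, call at D14, last visit at D52 (9.5.3.2); endpoint analysed per patient (9.6.3.1).

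**Step 1: the plan's own figure.** The protocol states: "For a sample size of 50 patients, the probability of observing at least one ADE will be 0.87 considering a probability of ADE of 0.04". Check: 1 − (1 − 0.04)^50 = 1 − 0.96^50 = 0.870. It reproduces, and it presumes that every ADE is captured.

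**Step 2: look-back windows.**

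| Period | Next scheduled AE question | Longest recall |
|---|---|---|
| After leaving D0 | D7 before treatment | 7 − 0 = 7 days |
| After leaving D7 (as planned) | D52 | 52 − 7 = 45 days |
| After leaving D7 (with a D14 question) | D14 | 14 − 7 = 7 days |
| After D14 (with a D14 question) | D52 | 52 − 14 = 38 days |

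The ratio is 45/7 = 6.4, and 45/52 = 87% of follow-up lies in the window with no scheduled question before its end. Forty-five days is the maximum; an ADE that starts late in the window is recalled over a shorter time.

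**Step 3: weight of one patient.** One patient is 1/50 = 2 percentage points. Exact 95% Clopper-Pearson intervals: 2/50 = 4.0% (0.5 to 13.7); 1/50 = 2.0% (0.1 to 10.6).

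**Step 4: effect on the 0.87.** Only patients whose sole ADE starts after they leave D7 can be lost through this gap. Let f be the share of ADE patients in that position and s the share of those captured at D52. The documents give neither, so both are assumed.

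- Recorded ADE probability: p = 0.04 × (1 − f(1 − s))
- Chance of at least one recorded ADE: 1 − (1 − p)^50

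| f | s = 0.9 | s = 0.7 | s = 0.5 |
|---|---|---|---|
| 0.10 | 0.867 (p = 0.0396) | 0.862 (p = 0.0388) | 0.856 (p = 0.0380) |
| 0.25 | 0.863 (p = 0.0390) | 0.848 (p = 0.0370) | 0.832 (p = 0.0350) |
| 0.50 | 0.856 (p = 0.0380) | 0.823 (p = 0.0340) | 0.782 (p = 0.0300) |

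Example, bottom right: p = 0.04 × (1 − 0.5 × 0.5) = 0.03, and 1 − 0.97^50 = 0.782.

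Across the assumed range the figure runs from about 0.87 to 0.78. With full capture (s = 1) it stays at 0.87.

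**The case against.** The case against making much of this is substantial, and most of it stands.

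- **Session 2 is not unobserved.** A reader might infer that everything after session 2 rests on 45-day recall. The documents do not support that: AEs and DDs are collected on site after session 2, following a full set of tests (Protocol 9.5.5.2). The gap begins when the patient leaves.
- **Volunteered events count.** Under 9.13.3 anything a patient mentions at the D14 call must be recorded. That creates a duty to record, though not a question. The D14 symptom form may also jog memory at D52, but it is not an AE enquiry.
- **Session 2 is not shown to look better tolerated.** A reader might infer this from the by-session tables. They count only ADEs dated D0 or D7, and both days have on-site collection, so they depend little on D52 recall. The remaining exposure is the imputation rule for forgotten dates.
- **A larger loss can be computed but is not justified.** If capture of 75% or 50% were applied to all ADE patients, the 0.87 would fall to 0.78 or 0.64. That would require every ADE patient's only ADE to start after leaving D7 (f = 1). Patients with an ADE recorded earlier already count.
- **No recall loss is documented.** The lists of anticipated ADEs are redacted, so onset and duration are unknown. Misdating alone does not change a yes/no endpoint.
- **No arm bias.** The schedule is the same in both groups.

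What remains is an avoidable stretch without a scheduled question on the primary endpoint, beside a call that is already planned.

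**Conclusion.** The concern holds for ADEs that start after the patient leaves D7. For these the first scheduled question is at D52, with up to 45 days' recall against up to 7 after session 1. Delayed, non-severe ADEs could be under-reported or misdated. That could bias the overall proportion with at least one ADE downwards and delay safety information, and an undatable event could be moved into the D0 table. It does not by itself bias 5 Hz against 10 Hz.

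The size cannot be derived from the documents. Under the assumed ranges (f from 0.10 to 0.50, s from 0.5 to 0.9) the 0.87 becomes about 0.87 down to 0.78, and each lost patient lowers the observed proportion by 2 points. This is a worthwhile, low-cost improvement to ascertainment of the primary endpoint. It does not invalidate the analysis.

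**What to change.** - In Protocol 9.5.5.3, state that at the D14 call the investigator asks about and records any AE or DD since the D7 visit.
- Mark D14 in the AE/DD row of Table 2 and of the synopsis schedule.
- In 9.5.5.4, collect AEs and DDs at D52 since the D14 call, which also settles what the last visit means.

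This gives each session the same 7-day first look-back and leaves 38 days to D52. It costs a few minutes in an existing call and one eCRF field. Collecting AEs by telephone is already accepted in 9.5.5.4, for patients who do not attend D52 in person.

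If follow-up is already complete, report the unequal look-back (7 against 45 days) as a limitation of the ADE estimate, and identify any ADE in the D0 table whose onset date was imputed.
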